4.1. Protocol Deviations

Important protocol deviations (including deviations related to study inclusion/exclusion criteria, conduct of the trial, patient management or patient assessment) will be summarized and listed for both the double-blind phase (Year 1) and observational phase (Year 2) separately [T11.13, T21.09, L11.07, L21.04]. The tables will display the number and percentage of subjects who experience any important protocol deviation and for each deviation type.

All protocol deviations that relate to COVID-19 will be summarized and listed for both the double-blind phase (Year 1) and observational phase (Year 2) separately [T11.14, T21.10, L11.07, L21.04]. The tables will display the number and percentage of subjects who experience any protocol deviation related to COVID-19.

Protocol deviations will be tracked by the study team throughout the conduct of the study in accordance with the Protocol Deviation Management Plan (PDMP). [Version 6].

- Year 1 data will be reviewed prior to unblinding and freezing the database to ensure all important deviations and deviations which may lead to exclusion from the analysis are captured and categorised on the protocol deviations dataset.
- This dataset will be the basis for the summaries and listings of protocol deviations.
- Year 2 data will be reviewed by the blinded study team prior to unblinding and freezing the database to ensure all important deviations are captured and categorised on the protocol deviations dataset.

All deviations will be discussed and adjudicated as important or not important according to the PDMP.

This preliminary assessment of the deviation resulting in the subject being excluded from the per protocol population, but will be subject to a final review as detailed in Section [4.2](#).

A separate summary and listing of all inclusion/exclusion criteria deviations will also be provided. This summary will be based on data as recorded on the inclusion/exclusion page of the eCRF [T11.12, L11.06].

4.2. Per Protocol Population

Periodic review of the per protocol population will be conducted during the course of the study, with a final assessment made prior to unblinding the data for the Year 1 reporting.

The per protocol population will be primarily based on an assessment of the important protocol deviations. However non-important deviations or other study conduct issues may be identified during the study that warrant a subject's exclusion from the per protocol population. This will be documented in the protocol deviation adjudication

meeting minutes prior to database freeze. Only protocol deviations or study conduct issues that have the potential to impact the efficacy evaluation will lead to exclusion from the per protocol population.

The per protocol population will be derived based on the Year 1 data. If Year 2 reporting (or combined Year 1&2) per protocol analysis is required it will be based on the per protocol population defined for Year 1.

Subjects excluded from the Per Protocol (PP) population will be summarized [T11.15].

5. CONSIDERATIONS FOR DATA ANALYSES AND DATA HANDLING CONVENTIONS

5.1. Study Treatment & Sub-group Display Descriptors

| Treatment Group Descriptions | | | |
|------------------------------|--------------------------|-----------------------------|--------------|
| RandAll NG | | Data Displays for Reporting | |
| Code | Description | Description | Order in TLF |
| A | Belimumab plus Placebo | BEL SC plus PBO IV | 1 |
| B | Belimumab plus Rituximab | BEL SC plus RTX IV | 2 |
| C | Belimumab Open-Label | BEL SC plus STD Therapy | 3 |

Treatment comparisons will be displayed as follows using the descriptors as specified:

1. BEL SC plus RTX IV vs BEL SC plus PBO IV
2. BEL SC plus RTX IV vs BEL SC plus STD Therapy
3. BEL SC plus PBO IV vs BEL SC plus STD Therapy

Table 1 Treatment Descriptors, Colors, Line Style and Symbols for Reporting in Double-Blind Phase

| Treatment Descriptor | Color | SAS Color | Line Style | Symbol |
|------------------------------|-------|-----------|-------------|-------------------|
| BEL SC plus PBO IV | Blue | CX0000FF | Dashed | Triangle (filled) |
| BEL SC plus RTX IV | Green | CX2A8307 | Long dashes | Circle (filled) |
| BEL SC plus Standard Therapy | Brown | CXA05000 | Solid | Square (open) |

5.2. Study Day

Study day is the number of days from Belimumab study treatment start date to the study day of interest and is calculated as:

| | |
|------------------------------------|---------------------------------------|
| Criteria: | Study day is: |
| Study date < treatment start date | Study date - treatment start date |
| Study date >= treatment start date | Study date - treatment start date + 1 |

Note: Study day cannot be zero. If either date is missing the study day is missing. Further detail is provided in Section [15.6.1](#)

5.3. Baseline Definitions

For all the endpoints for both the Week 52 and Week 104 analysis (except as noted in baseline definitions) the baseline value will be the latest pre-dose assessment with a non-missing value, including those from unscheduled visits. If time is not collected, Day 1 assessments are assumed to be taken prior to first dose and used as baseline.

| Parameter | Study Assessments Considered as Baseline | | Baseline Used in Data Display |
|---|--|------------------|-------------------------------|
| | Screening | Day 1 (Pre-Dose) | |
| Efficacy | | | |
| SLEDAI-2K Principal Investigator (PI) | X | X | Day 1 |
| SLEDAI-2K Independent Blinded Assessor (IBA) | | X | Day 1 |
| SLICC Damage Index | | X | Day 1 |
| Physician Global Assessment (PGA) | | X | Day 1 |
| Safety and Biomarker | | | |
| Laboratory assessments (including liver chemistry, serum immunoglobulin, Anti-dsDNA/ANA, and complement C3/C4) | X | X | Day 1 |
| Biomarkers (including Antiphospholipid antibodies, PBMC, B-Cells, BLys Protein, RNA for interferon, and immunogenicity) | | X | Day 1 |
| C-SSRS | X | X | Day 1 |
| PROs | | | |
| Patient Global Assessment (PtGA) | | X | Day 1 |
| FACIT-Fatigue score | | X | Day 1 |
| LupusQoL | | X | Day 1 |
| WPAI: Lupus | | X | Day 1 |

Baseline dose of corticosteroids is the 7-day average based on the 7 days **prior** to, but not including, treatment start date.

Concomitant medications are considered to be present at baseline if the start date is prior to Day 1 and the end date is on or after Day 1. Medications or events with a start date on Day 1 are considered as being on treatment (Section [15.4.1](#)).

Adverse events (AEs) are considered pre-treatment if the start date is prior to Day 1. AEs with a start date on or after Day 1 are considered as being treatment-emergent.

Baseline flares are flares that occur on or prior to the treatment start date. Therefore, flares that occur on Day 1 are not counted as post-baseline flares.

Unless otherwise stated, if baseline data is missing no derivation will be performed and baseline will be set to missing.

5.4. Multicentre Studies

In this multicentre global study, enrolment will be presented by country and investigative site. Countries will be grouped into geographic regions for summary presentation [T11.01] as shown in Section 5.5.2.

5.5. Examination of Covariates, Strata and Subgroups

5.5.1. Covariates and Strata

The list of strata is based on the randomization stratification and will be used in descriptive summaries and statistical analyses, some of which may also be used for subgroup analyses. Additional covariates and other strata of clinical interest have not been identified for planned analyses, but may be considered for post-hoc analyses.

| Category | Details |
|------------------------|--|
| Strata (As Randomized) | SLEDAI-2K: ≤ 9 vs. ≥ 10 Immunosuppressant: Use vs. Non-use Corticosteroid dose: ≤ 10 mg/day vs. > 10 mg/day |

The following covariates will be included in the analysis as detailed in Section 7 Efficacy Analyses

| Covariate | Details |
|---|--|
| SLEDAI-2K: ≤ 9 vs. ≥ 10 | Derived from the principal investigators' assessment at baseline (reference level: ≥ 10) |
| Immunosuppressant: Use vs. Non-use | Derived from reported concomitant medications at baseline (reference level: Non-use) |
| Corticosteroid dose: ≤ 10 mg/day vs. > 10 mg/day | Derived from reported concomitant medications at baseline (reference level: > 10 mg/day) |
| Covariates | No additional covariates |

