10. STATISTICAL CONSIDERATIONS

10.1. Hypotheses

The primary objective of the study is to demonstrate superiority (improvement in response rate) of co-administration of belimumab plus rituximab (Arm B: Combination) over belimumab monotherapy (Arm A: Control), when comparing the primary efficacy endpoint at Week 52 in subjects with SLE. An exploratory assessment of the relative performance of Arm A (control) and Arm B (combination) vs. standard SLE therapy (Arm C) will also be conducted.

The primary efficacy endpoint is defined as: the proportion of participants with a state of disease control defined as a SLEDAI-2K score ≤2, achieved without immunosuppressants and with corticosteroids at a prednisone equivalent dose of ≤5mg/day at Week 52.

Null Hypothesis (H_0): There is no difference between Arm B

(combination) and Arm A (control) in terms of the

primary endpoint at Week 52.

Alternative Hypothesis (H₁): There is a difference between Arm B (combination)

and Arm A (control) in terms of the primary

endpoint at Week 52.

A step-down sequential testing procedure will be used to control the overall type 1 error rate for comparing Arm B (combination) vs Arm A (control). With this procedure, the primary endpoint will be evaluated first and then the two major secondary endpoints (i.e., Clinical SLEDAI 2K score =0 at Week 64 next and then SLEDAI-2K score ≤2 at Week 104) for statistical significance based on the pre-specified sequence for interpretation. Specifically, endpoints will be tested in the sequence above (2-sided alpha=0.05) provided that statistical significance is achieved by all prior tests. If at any point in the

sequence statistical significance is not met, then subsequent endpoints in the sequence cannot be deemed statistically significant. Analyses of other efficacy endpoints will not be subject to any multiple comparison procedure.

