10.2. Sample Size Determination

In order to ensure adequate exposure for evaluation of safety, the study is designed with a target of 140 participants to be randomized into the combination arm. At least 280 participants will be randomised in this study, with a target of 70 participants in Arm A, 140 participants in Arm B and 70 participants in Arm C. This sample size provides at least 98% power (for the comparison of Arm B to Arm A at Week 52) at the 5% level of significance assuming the underlying response in the control arm is 10% and the true population effect is ≥25% with treatment Arm B (combination assumed response rate of 35%). The primary endpoint will be based on assuming study dropouts = treatment failures, and so the assumed responder rates for treatment Arms A and B already account for participant dropout rates. However, the sample size may be increased up to a maximum of 320 participants if the dropout rate, missing data or number of major protocol deviations suggests further participants are necessary to ensure robust conclusions can be drawn. Sample size was calculated using PASS 12 and is based in the Likelihood ratio test. No inferential tests are planned between Arm C and Arm A or Arm B; therefore no adjustment for multiplicity is required.

There are limited clinical data with therapies including both belimumab and rituximab. Based on elicitation of opinion from external experts, as well as the rarity of remission or disease control seen in published external studies and internal GSK review of previous belimumab data, a rate of 35% achieving a state of disease control (i.e., Arm B) is considered to be highly significant in SLE care. The assumed 10% responder rate in Arm A (control) at 52 weeks was estimated based on exploration of historical data from three comparable belimumab Phase 3 trials (IV: C1056 [BLISS-76] and C1057 [BLISS-52] and SC: BEL112341) in patients with SLE, albeit with some significant differences from this study in protocol inclusion criteria, control of background therapy for SLE, SLEDAI-2K derivation and treatment failure rules. The estimated Arm A

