2.1.4. Efficacy Tables

| Efficacy Tables | | | | |
|--------------------|-------------------|------------|--|---|
| New output number | Old output number | Population | Title | Major modifications since original RAP |
| Clinical Remission | | | | |
| 22.01. | 22.01 | MITT | Clinical Remission (IBA) at Week 64 (Hybrid) | |
| 22.02. | 22.02 | MITT | Logistic Regression Analysis of Clinical Remission (IBA) at Week 64 (Hybrid) | |
| 22.03. | 22.03 | MITT | Disposition of Clinical Remission (IBA) at Week 64 (Hybrid) | |
| 22.04. | NEW | MITT | Disposition of Clinical Remission (IBA) by First Reason for Non-Response at Week 64 (Hybrid) | 
 • New output (omission in original RAP) |

| Efficacy Tables | | | | |
|-------------------|-------------------|------------|---|---|
| New output number | Old output number | Population | Title | Major modifications since original RAP |
| 22.05. | 22.04 | MITT | Clinical Remission (IBA) and its Components at Week 64 (Hybrid) | 
 The planned component for 'Corticosteroid >0 to <=5mg/day' has been modified to match the actual component of the endpoint, i.e. "Corticosteroids at a prednisone equivalent dose of 0 mg/day" |
| 22.06. | NEW | MITT | Clinical Remission (IBA) and its Components by Baseline C3/C4 Level & Anti-dsDNA at Week 64 (Hybrid) | 
 New output (key subgroup of interest) The planned component for 'Corticosteroid >0 to <=5mg/day' has been modified to match the actual component of the endpoint, i.e. "Corticosteroids at a prednisone equivalent dose of 0 mg/day" |
| 22.07. | 22.08 | MITT | Clinical Remission (IBA) by Visit (Hybrid) (Year 2) | |
| 22.08. | 22.09 | MITT | Clinical Remission (PI) by Visit (Hybrid) (Year 2) | |
| 22.09. | 22.25 | MITT | Duration of Clinical Remission (PI) (Hybrid) (Year 1&2) | |
| 22.10. | 22.20 | MITT | Clinical Remission (PI) Sustained for at least 24 Weeks by Visit (Hybrid) (Year 2) | |
| 22.11. | 22.33 | MITT | Time to Clinical Remission (PI) Sustained for at least 24 weeks and maintained through to Week 104 [1] (Hybrid) | |
| Disease Control | | | | |
| 22.12. | 22.10 | MITT | Disease Control (IBA) at Week 104 (Hybrid) | |
| 22.13. | 22.11 | MITT | Logistic Regression Analysis of Disease Control (IBA) at Week 104 (Hybrid) | |
| 22.14. | 22.12 | MITT | Disposition of Disease Control (IBA) at Week 104 (Hybrid) | |

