15.6.3. SLEDAI-2K Total and Organ System Domain

| SLEDAI-2K Total and Organ System Domain Scores | | | | | | | | | | | |
|---|--|--------|------------|--------------|------------|--------|------------|------------------|--|--|--|
| 
SLEDAI-2K assessments consist of 24 individual items in which signs and symptoms, laboratory tests, and physician’s assessment for each of 9 organ systems are given a weighted score and summed if present (marked ‘Yes’) at the time of the visit or in the preceding 10 days. The maximum theoretical score is 105 (all 24 descriptors present simultaneously) with 0 indicating inactive disease (marked ‘No’).
 
Organ system domain scores are the sum of the weights of items within the organ domain as defined in Table 9.
 
In this study, proteinuria is evaluated using spot-urine protein [represented as protein-creatinine ratio or PC Ratio in the laboratory dataset]. in lieu of the 24-hour urine collection, as evaluated by the investigator.
 | | | | | | | | | | | |
| 
Table 9 SLEDAI-2K
 
  
 Organ System	Descriptor	Weight	Definition	
   
 CNS^a	 
CCI - This section contained Clinical Outcome Assessment data collection questionnaires or indices, which are protected by third party copyright laws and therefore have been excluded.
 	
  
 | | | | Organ System | Descriptor | Weight | Definition | CNS ^a | 
CCI - This section contained Clinical Outcome Assessment data collection questionnaires or indices, which are protected by third party copyright laws and therefore have been excluded.
 | | |
| Organ System | Descriptor | Weight | Definition | | | | | | | | |
| CNS ^a | 
CCI - This section contained Clinical Outcome Assessment data collection questionnaires or indices, which are protected by third party copyright laws and therefore have been excluded.
 | | | | | | | | | | |

| | |
|------------------------------|---|
| | CCI - This section contained Clinical Outcome Assessment data collection questionnaires or indices, which are protected by third party copyright laws and therefore have been excluded. |
| Vascular ^a | |
| Musculoskeletal | |
| Renal | |
| Mucocutaneous | |
| Cardiovascular & Respiratory | |
| Immunologic | |
| Constitutional ^a | |
| Hematologic ^a | |
| | |

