The clinical SLEDAI-2K score (Excluding Serological Activity assessments) is the sum of **22 of the 24** individual items from the SLEDAI-2K, excluding the following 2 items:

| | |
|-------------|---|
| Immunologic | CCI - This section contained Clinical Outcome Assessment data collection questionnaires or indices, which are protected by third party copyright laws and therefore have been excluded. |
| | |

The scoring of the 22 questions is weighted in the same manner as the SLEDAI-2K, however the maximum theoretical score is now 101.

Note that the wording in the Protocol was “Serological activity score, i.e., anti-dsDNA positivity and/or hypocomplementemia, is excluded from the Clinical SLEDAI-2K endpoint”. The endpoint has been clarified here by using the names of the two SLEDAI-2K item scores, however, this does not represent a change to the planned endpoint, just a clarification.

Partial but informative SLEDAI-2K score

If after imputation for missing questions the SLEDAI-2K total score is still not derivable due to missing individual questions, then the minimum possible score will be considered (sum of the answered questions).

Similarly a maximum possible score (observed questions + maximum response for missing questions) will be considered.

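### The Week 52 and Week 104 disease-control models omit baseline serology, a plausible predictor that is already collected; adding it would gain little power at the planned effect and up to about 5 points at a smaller one

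*SAP*

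**What the plan says.** Protocol section 4 states that serological activity is scored in the SLEDAI-2K used for the primary endpoint. RAP 15.6.3 says of the full 24-item score: "The maximum theoretical score is 105". Of the 22-item clinical version, with the two serological items removed, it says: "however the maximum theoretical score is now 101". Under RAP 7.1.1 a score above 2 is non-response.

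Protocol 10.4.1 and RAP 7.1.5.1 fit a logistic model with treatment, baseline SLEDAI-2K (≤9 vs ≥10), baseline immunosuppressant use and baseline corticosteroid dose (cut at 10 mg/day). RAP 7.3.5.1 repeats this model at Week 104. The covariate table in RAP 5.5.1 ends with "No additional covariates" and leaves any others to post-hoc work.

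Serology is not ignored elsewhere:
- RAP 5.5.2 defines a two-level variable: at least one low C3/C4 together with anti-dsDNA ≥30 IU/mL, vs not.
- RAP 7.1.5.1 plans Week 52 subgroup analyses by complement, by anti-dsDNA and by both combined, each with a treatment-by-subgroup interaction model.
- The July 2021 addendum, section 2.1.4, adds tables by this variable at Weeks 64 and 104, labelled "New output (key subgroup of interest").

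**The concern.** Participants with both serological items present at the assessment are non-responders however quiet their clinical disease. Entry does not require positive serology but scores it if present (protocol 6.1), so the population is mixed. If baseline status persists to some degree, it separates participants with a lower chance of response from the rest. Leaving a prognostic variable out of a logistic model costs some power, and a chance imbalance between 70 and 140 participants goes uncorrected, because serology is not a stratification factor.

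The RAP does add the relevant baseline value for other endpoints: SLICC score (7.6.5), PGA and continuous SLEDAI-2K (7.9.6), FACIT-Fatigue (9.2) and biomarker baselines (10.1). The confirmatory disease-control models have no such term for serology.

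**Working it through.** **1. Does serology block response?** The two items together carry 105 − 101 = 4 points. Both present means a score of at least 4, which exceeds 2, so disease control is impossible at that visit. The separate item weights are blacked out, so only the sum can be derived. The block applies to serology at the visit; the candidate covariate is serology at baseline.

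**2. The plan's own power.** Protocol 10.2 works "with a target of 70 participants in Arm A, 140 participants in Arm B and 70 participants in Arm C", with 10% vs 35% and two-sided 5%: "This sample size provides at least 98% power". Pooled z test:
- p̄ = (70×0.10 + 140×0.35)/210 = 56/210 = 0.2667
- SE under H0 = √[0.2667×0.7333×(1/70 + 1/140)] = 0.0647
- SE under H1 = √[0.10×0.90/70 + 0.35×0.65/140] = 0.0540
- z = (0.25 − 1.96×0.0647)/0.0540 = 2.28, power 98.9% (exact likelihood-ratio test 99.0%)

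The stated figure reproduces. The same formula at 10% vs 25% gives z = (0.15 − 1.96×0.0586)/0.0512 = 0.69, power 75.4%, against 75% in protocol Table 5.

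**3. Effect of adding the baseline indicator.** The documents give neither the prevalence of double positivity (q) nor its odds ratio (OR) for response, so both are assumed. Simulation used 70 vs 140 participants and 4,000 trials per cell, with marginal rates held at the protocol values. Wald power, in %:

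| Rates | q | OR | Without | With | Change, points |
|---|---|---|---|---|---|
| 10 vs 35 | 30% | 1.0 | 98.6 | 98.5 | −0.1 |
| 10 vs 35 | 30% | 0.25 | 98.7 | 98.9 | +0.2 |
| 10 vs 35 | 30% | 0.1 | 98.6 | 99.1 | +0.5 |
| 10 vs 35 | 50% | 0.25 | 98.3 | 98.8 | +0.5 |
| 10 vs 35 | 50% | 0.1 | 99.2 | 99.5 | +0.3 |
| 10 vs 25 | 30% | 1.0 | 75.3 | 75.2 | −0.2 |
| 10 vs 25 | 30% | 0.25 | 75.6 | 76.6 | +1.0 |
| 10 vs 25 | 30% | 0.1 | 74.6 | 78.1 | +3.6 |
| 10 vs 25 | 50% | 0.25 | 75.5 | 78.1 | +2.6 |
| 10 vs 25 | 50% | 0.1 | 75.5 | 81.3 | +5.7 |

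Changes come from unrounded values. The Monte Carlo standard error of a single power is about 0.2 points near 98 to 99% and 0.7 near 75%; paired differences are tighter.

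Separate likelihood-ratio runs at 10% vs 25%:
- q 35%, OR 0.35: 77.6 to 78.5
- q 35%, OR 0.2: 79.6 to 80.8
- q 50%, OR 0.2: 78.6 to 81.8
- q 50%, OR 0.1: 79.2 to 84.5

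Type I error was 5.5 to 5.6% and unchanged by the term. Its simulation standard error is √(0.05×0.95/4000) = 0.34 points, so this is within noise of 5%.

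**4. Overlap with the SLEDAI-2K covariate.** Baseline total SLEDAI-2K already includes the serology points, but enters only through the ≤9/≥10 cut. With double positivity set at 35% in the low and 65% in the high stratum (3,000 runs, likelihood-ratio test, 10% vs 25%), power rises from 77.2 to 80.1% at OR 0.2 and from 79.8 to 83.8% at OR 0.1. Without overlap it rises from 77.6 to 80.5% and from 78.9 to 83.5%. Across the scenarios with overlap, the gain was +0.1 to +0.6 points at 10% vs 35% and about +0.3 to +4.6 at 10% vs 25%. With a non-prognostic indicator the loss was at most about 0.4 points (0.5 in one likelihood-ratio cell of the runs without overlap, within noise).

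**5. Upper bound.** Suppose no double-positive participant responds in either arm. At q = 50% the comparison becomes 35 vs 70 participants at 20% vs 50%, with power 86.9% against 75.4%, a gain of 11.5 points. Over q = 20 to 50% the gain is 2.8 to 11.5 points at 10% vs 25% and 0.5 to 1.1 at 10% vs 35%.

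**6. Chance imbalance.** At q = 50% the standard deviation of the between-arm difference in prevalence is √[0.25×(1/70 + 1/140)] = 0.073. A difference of 10 points or more then has probability of about 17% (normal approximation, ignoring stratification).

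**The case against.** The case against is substantial.

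- **Size.** The trial was planned at 10% vs 35%, where the gain is under 1 point. This stands. The larger figures belong to 10% vs 25%, which is a scenario in protocol Table 5 and not the planning assumption.
- **Baseline is not the visit.** Both arms receive belimumab, and RAP 10.2 plans tables of shifts in complement and autoantibodies. A reader might infer from the 4-point arithmetic that baseline serology is a strong predictor. The documents do not show that: they give no figure for persistence.
- **No validity defect.** A reader might also infer that the present odds ratio is biased. It is not. The model estimates an odds ratio conditional on three factors; adding a fourth changes the conditional odds ratio being estimated, because odds ratios are not collapsible. Adjusting for the stratification variables is legitimate.
- **Already examined.** The planned subgroup and interaction models contain serology and deserve acknowledgement. They describe the effect by stratum but do not adjust the confirmatory test, so they do not answer the point.
- **Hindsight.** The key-subgroup label dates from after the first database lock and primary analyses, and one of the tables it marks concerns Week 64. It is no evidence of what should have been pre-specified. The point rests on the scoring rule and on RAP 5.5.2.
- **Sparse data.** About 0.10×70 = 7 control responders are expected. At q = 30% and OR 0.1, 2 to 8% of simulated trials had no double-positive responder. The existing rule that drops a non-converging factor covers this, but the term is then least secure where it would help most.

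**Conclusion.** The point holds as a modest efficiency improvement. The scoring rule makes baseline serology a plausible predictor of disease control; the variable exists, and the confirmatory models leave it out. With 35 to 50% of participants double-positive and an odds ratio of 0.1 to 0.35, adding it gains well under 1 point of power at 10% vs 35% and roughly 0 to 5 points at 10% vs 25%. The downside if serology is not prognostic is about 0.4 points, and type I error is essentially unaffected. Prevalence, strength and persistence are all assumptions. The documents do not support saying that the trial is underpowered for want of this term, that its odds ratio is biased, or that the plan overlooks serology.

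**What to change.** Pre-specify the RAP 5.5.2 indicator (at least one low C3/C4 and anti-dsDNA ≥30 IU/mL at baseline, vs not) as one extra term in the Week 52 and Week 104 disease-control models. Amend RAP 5.5.1, 7.1.5.1 and 7.3.5.1, and protocol 10.4.1, which fixes the three covariates. Do not add it at Week 64, where serology is excluded from the score. Report the three-covariate model alongside, because the two conditional odds ratios differ, and keep the convergence rule. State whether the stratified Cochran-Mantel-Haenszel difference and the COVID-19 imputation models, which use the same three factors, stay as they are.

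The cost is wording in two documents and one parameter, with 7 + 35 = 42 responders expected at 10% vs 25% and 7 + 49 = 56 at 10% vs 35%. No new data are needed. The October 2020 addendum preceded database release, so the change could have been pre-specified then. The July 2021 addendum follows the primary analyses; if the term is added after that point, label the adjusted results as supportive and leave the confirmatory test unchanged.
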